7.3.3. Physical education (PE)

The TAAG PE objectives are to: 1) provide a PE experience where girls are engaged in MVPA during 50% of class time; 2) provide a PE experience where girls experience many opportunities to successfully participate in a choice of activities, increase their competence in skill development and health-related fitness, and enjoy physical activity during PE class; and 3) encourage girls to participate in physical activity outside of PE class, including after school programming.

The first two objectives are reached by positively influencing how PE class is conducted including the format of lessons, class management strategies, instructional strategies and the development of social skills that reduce barriers to girls' participation and enjoyment of physical activity. Enjoyment of PE class is enhanced by providing choice to students, including choice of activities, choice of competitive levels and where possible, choice of gender segregated activities. Sample lessons and unit activities are presented during staff development training and in the written materials giving PE staff concrete examples of active lessons and activities. Because most PE classes include both boys and girls, the ideals of TAAG apply to the instruction of all students in class.

The third objective is reached by engaging PE teachers as links to the wider school and community physical activity opportunities that are being offered as part of the TAAG intervention. In some cases, PE teachers also deliver the TAAG Health Education with Activity Challenges lessons positioning them to reinforce activity beyond PE class. PE

teachers promote TAAG after school activities and other TAAG-supported community programs.

TAAG PE intervention strategies:

TAAG PE is not a traditional curriculum, rather it uses a staff development model, training and empowering schools' PE teachers to adapt or revise their current curriculum in ways that increase MVPA and girls' satisfaction with the PE experience. There are two primary intervention strategies for TAAG PE: staff development training and on-site follow-up. TAAG Field Center intervention staff conduct one full day training and several booster in-service trainings to all PE teachers in the intervention schools in each of the TAAG intervention years. PE specialists from all three intervention schools at each Field Center are trained together, enhancing group support, role modeling and problem solving between the PE teachers. These in-service trainings are active trainings, modeling the TAAG intervention concepts and providing the PE teachers with experiential learning. Topics that are covered in training include: gender equity in physical activity, barriers girls encounter in being physically active, adapting existing lesson plans to meet the TAAG PE objectives, introducing more choice into PE lesson plans and reducing non-active time during PE.

Following initial training, TAAG Field Center intervention staff provide regular, on-site follow-up. The purpose of these visits is to provide support for the adoption and institutionalization of TAAG PE. This consultation includes feedback, modeling, and technical support to PE teachers.

TAAG PE materials:

Materials developed for TAAG PE are a TAAG PE Resource Manual, TAAG PE Activity Box, and Task Cards for use by school staff, and a Manual of Operations for TAAG Field Center staff. The TAAG PE Resource Manual is given to staff at the first staff development training and includes: 1) an overview of TAAG; 2) the rationale, vision, and objectives of TAAG PE; 3) recommended lesson format; 4) tips on building a positive learning environment; 5) information on health-related fitness; 6) physical activity promotion beyond PE; 7) planning and assessing for progress; 8) commonly asked questions; 9) resources and professional information; and 10) references.

The TAAG PE Activity Box provides a wide variety of sample unit activities focusing on health-related fitness such as aerobic games, bench aerobics, power walking, and resistance and strength training. These sample unit activities give concrete examples to teachers on how to adapt their current units to meet TAAG objectives and examples of new units to introduce to their classes. The Task Card file contains handouts, task cards and a CD to assist with implementing the TAAG sample activities.

The TAAG PE Manual of Operations is a manual for Field Center intervention staff that describes the implementation of the PE component, including staff development objectives, objectives, and agendas for staff development training and booster sessions, process evaluation measures, and guidance on interacting and collaborating with teachers.

Implementation of TAAG PE:

After randomization but prior to the first intervention year (Spring 2003), the PE teachers convene in each intervention school for a TAAG orientation session that provides an overview of TAAG and the TAAG intervention. At this session, Field Center investigators assist the PE teachers in developing a timeline for the next school year's intervention activities, discuss their role in the TAAG intervention and set up dates for the first staff development training. School PE equipment is inventoried and orders placed to purchase needed equipment for the next school year.

All PE teachers in the intervention schools are trained and supported to implement TAAG PE. Training of all PE teachers in a school, rather than just those teaching the 7th and 8th grades, enhances the possibility that TAAG PE principles are adopted by the school's entire PE department, increasing the chances for institutionalization.

The first staff development training is conducted immediately prior to the beginning of the school year (August or September 2003). TAAG Field Center staff conduct the training. One or two half-day booster training are conducted each school year. Topics for the booster trainings may include strategies on motivating girls, which includes providing choice and positive socialization, incorporating cooperative learning into PE classes and strategies to encourage participation in out-of-school activities.

Following the formal training, on-site visits begin. Field Center intervention staff visit each school at least twice each month, observe PE class and arrange for an informal discussion with the PE teachers about problem-solving, increasing activity or participation in lessons, and progress towards reaching the TAAG PE objectives. During these on-site visits, intervention staff may help demonstrate how a new TAAG activity works, help the PE teacher adapt a previous lesson to help it meet TAAG objectives, or help to create more choice options in PE class so girls have more opportunities to find enjoyable, active options. Working toward gender equity and reducing gender bias is an important goal stressed both in trainings and during on-site visits.

7.3.4. Programs for physical activity

The TAAG Programs for Physical Activity component draws from Organizational Change Theory and direct action community organizing in developing a process by which schools, communities, and the TAAG intervention staff form partnerships to accomplish a common goal of increasing girls' participation in physical activity at school and outside of the regular school day. A unique aspect of this partnership is that it school-based rather than state or other community-institution-based. It may be argued that using the school as the hub of the partnership limits its scope and reach. However, since schools are the primary institutions in the community that focus on youth needs, and since schools are relatively stable institutions with a constant mission, we believe that this model has great potential to be effective in resulting in more physical opportunities for girls locally and may serve as the impetus for wider community change that expands beyond the local school. School district or state-level policy change (i.e., district or state-level requirements for daily PE, state or district level funding for transportation or programming) may occur as a result as the demonstrated successes of the school-based activity partnerships. The objectives for the TAAG Programs for Physical Activity are to:1) provide and promote physical activity programs during the school day, after school, on the weekends, and during the summer in both school and community-based venues; 2) provide a minimum of 30 minutes of MVPA during each program period of TAAG-sponsored activities; and 3) work to advance school-wide change including policy change, that promotes and supports physical activity.

Programs for Physical Activity intervention strategies:

For each school catchment area, the school-community-university partnership works to increase the number of available and/or accessible programs in the school and in the community. These programs might be new programs that are developed as part of TAAG intervention activities or might be modifications or special promotions of existing programs. The TAAG Programs for Physical Activity also works towards decreasing barriers, improving access to programs, promoting attendance, and reinforcing participation in programs and activities. The goal of the partnership process is to develop a shared vision and purpose among a diverse group of stakeholders so that this group may work toward the common goal of increased physical activity opportunities for girls in the school and community.

The Programs for Physical Activity objectives include enhancement of physical activity opportunities both outside of school and during the school day. Increasing the availability of out of school programming is a formidable task for schools with significant challenges in transportation, space, personnel, and financial resources. Partnering with other community agencies and individuals to provide help and resources is a logical solution, but one that most schools have difficulty initiating. TAAG Programs for Physical Activity builds partnerships between school and community agencies and individuals, providing strong and sustainable links between schools, girls, and community.

The types of out-of-school programs as well as the number and type of partners are involved are expected to vary widely from site to site. Our objective is to standardize the process as much as possible, while allowing the partners to develop plans that best meet the needs and desires of girls and schools in their community. The programs that are promoted through the Programs for Physical Activity might be new programs or existing programs that are modified to meet TAAG objectives. Programs supported by Programs for Physical Activity are all supervised programs, and provide a variety and range of physical activity choices, from very structured to unstructured, competitive to leisure time activities, for the very athletic and for the very inactive. Partners may contribute in a variety of ways including: offering direct programming in a community agency, such as a new kickboxing class at the YWCA advertised to TAAG girls; offering direct programming in the school after hours, such as a jazzercise instructor in the community offering a new class after school; or supporting physical activity in other ways, such as a health maintenance organization providing funds for transportation to a community center or providing funds for bike racks at the school.

Realizing that convening and mobilizing community groups takes time, and, facing the reality that out-of-school programming must begin quickly in this two-year intervention trial, information collected during the formative assessment phase and from one-on-one interviews are used to generate a jump-start menu of out-of-school programs that can be promoted as TAAG activities in the fall of 2003. These jump-start activities not only provide some programming immediately, but also give the Programs for Physical Activity some concrete examples of the types of programming that the partners might implement and provide the model for a proactive and vital partnership that produces a tangible and important outcome.

In addition to out-of-school programming, Programs for Physical Activity also considers ways to increase activity options during the school day and to reduce barriers to TAAG intervention objectives. Programs for Physical Activity subgroups that focus on inschool issues are modeled after school advisory groups advocated by Centers for Disease Control (Centers for Disease Control and Prevention, 2000a) and NASPE (NASPE Middle and Secondary School Physical Education Council, 2000) for helping to create school-wide change, including policy change. A menu of possible in-school Programs for Physical Activity projects might include:

- Develop a system for storing and checking out PE equipment so that after-school programs can use PE equipment;
- Organize a "TAAG Girl of the Week" recognition event;
- Organize a lunch time activity fair with games and special events;
- Help problem-solve how to deal with the loss of the activity bus due to budget cuts;
- Work on a petition to the school district for daily PE.

Materials for Programs for Physical Activity:

The materials for this component include a Manual of Operations for TAAG Field Center staff on how to help create and maintain the partnership. Materials for school and community partners include materials and support, such as the a summary report of formative assessment information, start-up funds information, an action planning document, mini-grant applications, and materials describing methods of collaboration and support.

Implementation of Programs for Physical Activity:

The Programs for Physical Activity process begins immediately after randomization with a goal of having programming begin by the fall of the first year of the intervention either through Jump-Start Activities or in conjunction with activities implemented as a result of the partnership decisions. The number of programs is anticipated to grow rapidly during the first year and by the second year of the intervention daily programs or opportunities can be identified that are a result of the Programs for Physical Activity. Programming is anticipated to occur during the summer between the first and second year of the intervention. We start the partnership development by compiling formative assessment information from the school, community agencies, girls, and parents and by conducting one-on-one interviews in the community. One-on-one interviews are conducted by TAAG intervention staff with a variety of stakeholders in the community (e.g., school personnel, community agency personnel, private business owners, and parents) to hear their perspectives on the issue and to assess their interest and potential commitment to being involved in the partnership.

The TAAG Field Center interventionist compiles information gathered from the formative assessment and the one-on-one interviews into a Summary Report. This is a brief overview of current physical activity opportunities in the school and community for use in educating and motivating potential partners. A first meeting of the potential partners (identified through formative assessment and one-on-ones) is convened. At a minimum, one school, community, and a TAAG intervention staff member make up the initial Planning committee. Other interested stakeholders may be involved as programming objectives are set and operationalized. The Summary Report is shared and other stakeholders are identified.

Once the set of partners is determined, empowerment of the partnership is substantiated by the provision of start-up funds for the partnership. These funds are provided by the university partner and are used as seed money to begin projects delineated by the partnership. The partners begin developing recruitment and retention plans and considering ways to deal with challenges in programming such as transportation and costs. The Programs for Physical Activity meets as a large group at least twice a year. Much of the work of the Programs for Physical Activity is expected to occur in subcommittees or as smaller action planning teams.

As the partners move into the action phase, they develop and carry out plans for programs and enhanced opportunities. This includes identifying and preparing staff for specific programs; tending to program implementation details such as location, scheduling, facilities, and equipment needed; addressing safety and supervision issues; addressing barriers to participation; recruiting participants, carrying out programs, and monitoring programs. One mechanism to be used to encourage innovative programming is the mini-grant. The mini-grants provide small stipends of money to individuals, school or community groups to facilitate a programming idea. The partnership would oversee the grant process and make awards.

As the ongoing implementation step, the TAAG Programs for Physical Activity assesses progress, revisits goals and plans as needed, maintains and expands existing programs and opportunities, implements new ideas and recognizes and celebrates success. Elements of process evaluation and formative assessment findings are shared with the partners to give them feedback on girls' responses to programming; challenges encountered and need for additional programming. The Summary Report from baseline is updated periodically and reviewed by the group to help evaluate their progress.

7.4. Implementation of the TAAG intervention and quality control

A Memorandum of Understanding signed during school recruitment delineates the intervention activities that schools must agree to facilitate or conduct if randomized to the intervention condition. After randomization to the intervention condition, TAAG Field Center staff meet with the school administrator and other school staff to determine communication channels and procedures for coordinating, organizing and implementing TAAG intervention activities in the school. Implementation of community-based TAAG intervention activities is coordinated through the Programs for Physical Activity. The coordination of TAAG intervention activities may vary from school to school and site to site in order to meet local needs.

The TAAG Field Center staff are responsible for assessing and monitoring the quality of the intervention components. The quality of the TAAG intervention activities are maintained through regular interaction between the TAAG intervention coordinator and designated school personnel and groups involved with intervention activities, through use of standardized training and intervention materials and manuals, and through process evaluation documentation and review of data (See Process data, Quality control, section 10.5)

7.5. Use of formative assessment and pilot testing in planning the TAAG intervention

7.5.1. Formative assessment

The Intervention Subcommittee and working groups conducted formative assessment during the development of intervention plans. As formative assessment results became available, they were shared with the intervention subcommittee and working groups by both written and oral presentations. Intervention plans were revised and refined accordingly. See section 6 for more information on Formative Assessment results and recommendations.

7.5.2. Intervention pilot testing

TAAG PE, TAAG Health Education with Activity Challenges and selected elements of TAAG Promotions are piloted beginning in the fall of 2002. Training of the trainers for these pilot elements is scheduled for early fall of 2002 and training of the pilot schools is scheduled for fall of 2002. Passport and Pedometer activities for TAAG Promotions are piloted in winter 2002.

The pilot testing of the Programs for Physical Activity includes two components. Each site works with a pilot intervention school using the protocol described above to develop community partners. Training for the partnership process occurred in February 2002. In addition, as part of the pilot work, each Field Center piloted at least one activity for girls in either a school or community setting. The purpose of this element of the pilot was to give sites experience in facilitating the enactment of activities and getting practice and experience in promoting activities. Some of the activities piloted were: girls boxing, training for running or walking a community 5K race, a dance and drama program, girls

3-on-3 basketball, hip-hop dancing, and cardiofunk dancing. These programs were implemented drawing from local resources or community agencies.

The intervention timeline is developed so that there is some time between the end of the pilot activities and the completion of all the formative assessment and the final development of materials for the main trial.

7.6. Working toward institutionalization: A Program Champion approach

The TAAG 8B measurements evaluate the extent to which environmental changes have been maintained in TAAG schools and communities after the end of the active TAAG intervention activities by assessing elements of the school and community environments and by evaluating student-level outcomes in a cross-sectional sample of 8th grade girls.

In year 2 of the intervention (2004-2005) we will develop a process to identify and train school and community program champions as an intervention strategy to support the institutionalization of TAAG intervention components. The concept of a program champion is not new to school-based health promotion programs. However, the majority of the research on program champion is post hoc; when identifying factors related to the institutionalization or sustainability of programs frequently a "self-appointed" program champion emerges as a key factor in sustaining the intervention. TAAG will develop a process to identify potential program champions during the active intervention phase and will work with them to implement and adapt TAAG intervention strategies so that they will be sustainable after the active intervention phase of TAAG.

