Identifying the social ecological and other factors that influence physical activity behavior in youth is an important prerequisite for designing effective interventions for this population (Baranowski, 1997, Baranowski, 1998). As a result, a great deal of research has focused on identifying the psychosocial and environmental determinants of physical activity in youth. Collectively, this body of research has identified physical activity self-efficacy, perceived barriers, outcome expectancies, enjoyment, social norms, time spent outdoors, involvement in community-based agencies that promote physical activity, access to equipment and facilities, parental encouragement, and parental activity as factors associated with youth activity behavior (Sallis, 2000c). Although these findings have helped researchers focus intervention strategies on specific targets, very few studies in this area have utilized longitudinal study designs, making it impossible to infer temporal sequencing and causal relationships between the hypothesized determinants and physical activity behavior. Moreover, few intervention studies have documented that intervention strategies result in positive changes in the determinants of physical activity and that these changes account for changes in physical activity behavior. Finally, studies rarely examine the permanency of environmental changes that may cue physical activity not only within a given cohort but for future groups of individuals as they pass through their school years or spend extensive time in other behavior settings.

TAAG presents the opportunity to determine whether these ostensible mediators of change indeed are influenced by a comprehensive intervention, and lead to behavior change. TAAG's emphasis on the physical and social environments that set the stage for physical activity leads us to emphasize the maintenance of environmental and behavior change.

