The sustainability of the TAAG intervention is determined by assessment of a crosssectional sample of girls in the 8th grade one year after the end of the intervention in spring of 2006. These results are compared to those in the cross-sectional sample of 8th grade girls examined in the previous year while the TAAG intervention was on-going. This comparison determines whether the effects of the intervention are maintained in the TAAG schools one year after the active intervention has ceased.

Minutes per day of MVPA (unweighted by METS), physical fitness, body composition, types and context of physical activity, physical activity in PE, self-reported physical activity related variables and environmental outcomes are assessed at baseline and at the end of the 2-year intervention. These time periods are designated in this document

as 6 (baseline) and 8A (spring of 2005). Minutes of MVPA and environmental outcome variables (described in section 10) are also measured at the time of the second assessment of 8th grade girls in the spring of 2006 (designated here as 8B). Additional measurements to be obtained at that time (8B) are determined based on the analyses of the effect of the intervention assessed in spring of 2005 (8A). Higher priority is given to the measurement of variables that were different among intervention versus control girls and schools at the end of the intervention period. In addition, financial considerations influence the number of variables that can be measured.

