7.3.2. Health education with activity challenges

TAAG Health Education with Activity Challenges provides youth with the knowledge and skills needed to be more active both inside and outside of school. Parallel lessons with the same learning objectives are designed for both classroom and physical education settings, allowing schools to decide where TAAG Health Education with Activity Challenges best fits with their school's curricular needs. Innovative Activity Challenges enhance each lesson and provide opportunities for students to be active and have fun while learning. Because most health education instruction occurs in co-educational classes, TAAG Health Education with Activity Challenges is designed for both girls and boys.

The objectives of TAAG Health Education with Activity Challenges are to: 1) develop behavioral and communication skills to increase physical activity; 2) increase awareness and utilization of community-based physical activity resources; and 3) promote the enjoyment of physical activity.

Health education with activity challenges intervention strategies:

TAAG Health Education with Activity Challenges is a multi-lesson health education curriculum for 7th and 8th grade. Each year of the intervention includes lessons, an associated activity challenge to be done outside of class and brief follow-up sessions. Each lesson is designed to take between 30-45 minutes to teach. There is a brief follow-up session (taking about 10 minutes) of the next TAAG lesson to review progress on the Activity Challenge that was assigned in the main lesson. The lessons have a scope and sequence with one lesson building on the previous one and year two lessons

building on year one lessons. Teachers are trained to teach all lessons in the appropriate sequence. Included in the health education lessons are topics such as the benefits of physical activity, enlisting social support for being active, setting goals for activity, reducing barriers to being active, and self-monitoring techniques for assessing physical activity.

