9.6.1. Age and grade

Background and rationale

Documentation of age and grade will be necessary for describing study participants.

Objectives

To assess age, grade, PE class enrollment, and duration of enrollment at the TAAG school for the purpose of describing the sample.

Methods

Age is reported in the consent form. Grade is assessed as part of the Student Questionnaire. They are also assessed during the second 8th grade year. The age question presents a space for date of birth to be written. PE class and school enrollment are assessed as part of the Student Questionnaire. The two PE class enrollment questions, answered by Yes or No, address when the girl took PE. The school enrollment question asks the girl to identify the grade at which she started attending her current middle school.

9.7. **Measurement logistics**

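### The pooled 8B difference answers whether effects persist in 8th grade girls, but most of those girls attended the schools in the active years, so it cannot by itself show that the environment was maintained

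*Protocol*

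**What the plan says.** Section 7.6 opens with "The TAAG 8B measurements evaluate the extent to which environmental changes have been maintained in TAAG schools and communities". It names two means: direct assessment of the school and community environments, and the evaluation done "by evaluating student-level outcomes in a cross-sectional sample of 8th grade girls". Section 4.1 is worded differently: "The sustainability of the TAAG intervention is determined by assessment of a crosssectional sample of girls in the 8th grade", and of the comparison of 8B with 8A it says "This comparison determines whether the effects of the intervention are maintained in the TAAG schools one year after the active intervention has ceased". Section 2.7 explains the interest in lasting environmental change, which should cue activity "not only within a given cohort but for future groups of individuals as they pass through their school years". In section 3.2, aim 9 asks whether effects are maintained in 8th grade girls a year later, and aim 10 asks whether the intervention itself is maintained.

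On who was exposed, section 7.6 and the sample school agreement in Appendix 3 place active delivery in school years 2003-04 and 2004-05. Section 5.1 requires schools that house grades 6 to 8. Section 7.3.3 describes "Training of all PE teachers in a school, rather than just those teaching the 7th and 8th grades" as a way to raise the chance of department-wide adoption. Section 7.3.2 says "TAAG Health Education with Activity Challenges is a multi-lesson health education curriculum for 7th and 8th grade". Section 9.6.1 says "The school enrollment question asks the girl to identify the grade at which she started attending her current middle school", and gives the purpose as describing the sample. Table 9.1 lists this item at 8A and 8B.

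**The concern.** Section 7.6 uses the activity of 8B girls as evidence that environmental change was kept. That reading is clean only if those girls met nothing but what the school had kept. The protocol's calendar puts most of them in the intervention schools while the program was being actively delivered, and no section says so.

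The error can run in two directions. A positive 8B difference could be credited to a maintained environment when it is persistence in girls treated earlier. A smaller difference at 8B than at 8A could be called failed maintenance when the two groups simply had different doses: grades 7 and 8 for 8A, grades 6 and 7 for 8B. Section 14.3 calls sustainment one important secondary hypothesis, so the interpretation matters even though the primary 8A analysis is untouched.

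**Working it through.** **Inputs.** Two-year attrition 36% (section 14.5.4; section 5.1 caps it at 35%). One-year transiency cap 28% (section 5.1). Refusal 20%, 120 girls invited per school at follow-up, SD 94.9, ICC 0.01, projected effects 15.6 and 9.4 MET-minutes, 18 schools per arm (section 14.5.4, Table 14.1). Error degrees of freedom 28 (Appendix 4). Stable class size is an assumption: leavers are replaced one for one.

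**The plan's own retention figure.** Appendix 4 (A.4.6.2) gives 49 cohort girls per school with 120 selected and 25 with 60 selected.
- 120 × 0.64 × 0.80 × 0.80 = 49.2
- 60 × 0.64 × 0.80 × 0.80 = 24.6

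Both reproduce, so 64% retention from 6th to 8th grade is the plan's working value.

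**Calendar.** 8th grade in spring 2006 means 7th grade in 2004-05 and 6th grade in 2003-04, exactly the two active years.

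**Share of 8B girls exposed.**
- Both active years: 1 − 0.36 = 64% (65% at the 35% cap). Counted from fall of 6th grade, 2.5 years at the same rate: 0.64^1.25 = 57% (0.65^1.25 = 58%).
- At least one active year: 1 − 0.8² = 0.36, so about 20% leave and are replaced each year, and about 80% were present in 7th grade. That is 0.8 × 96 = 77 of the 96 girls measured per school (120 × 0.8). At the 28% one-year cap it is 72%.
- The 64% falls to 50% only if classes grow by 28% through in-migration: 0.64 / 1.28 = 0.50.

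**Illustration of carry-over.** The document gives no carry-over fraction, so let f be the assumed fraction of the 15.6 effect that persists in the 64%, with nothing maintained in the school. The 8B difference is 0.64 × f × 15.6. The blended 8A effect implied by the plan is 0.64 × 15.6 + 0.36 × 9.4 = 13.4.

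| f | 8B difference (MET-min) | share of 13.4 |
|---|---|---|
| 0.25 | 2.5 | 19% |
| 0.50 | 5.0 | 37% |
| 0.75 | 7.5 | 56% |
| 1.00 | 10.0 | 75% |

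A visible 8B difference is therefore possible with no maintained environment at all.

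**Precision of an estimate in new entrants.**
- Entrants: 0.2 × 96 = 19.2 per school, × 36 = 691 girls.
- Variance of a school mean: 94.9² × (0.01 + 0.99/19.2) = 554.
- SE of the difference: √(2 × 554 / 18) = 7.85 MET-minutes.
- Power on 28 df: about 21% for 9.4 and 48% for 15.6.
- With 28% entrants, the SE is 6.85 and power is 26% and 60%.

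This supports an estimate with a wide interval, not a test.

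**The case against.** The strongest reply is that 8B already delivers the girl-level quantity the protocol asks for. Aim 9 and section 14.3 speak of effects sustained in 8th graders a year later, and the randomized school contrast answers that whatever the mechanism. This stands. A reader might infer that the 8B comparison is invalid or biased; the documents do not support that.

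A reader might also infer that section 4.1 equates girls' activity with a maintained environment. It does not: it speaks of the intervention and its effects. The link to the environment is made in 7.6, where direct environmental measurement is named first. Nor does any section rest aim 10 on the pooled girl-level result. Class structure, programs, partnerships and policies are all measured at 8B (sections 10.2 and 10.3), and several process instruments continue then (section 11.3).

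It would also be too strong to call 8B a second fully treated cohort. Training all PE teachers is said only to raise the chance of wider adoption. The health lessons are for 7th and 8th grade, so 8B girls had at most the 7th-grade part in the active phase.

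Finally, the limitation is inherent in a one-year follow-up of 8th graders in grade 6-8 schools, and an analysis by entry grade may properly sit in a statistical analysis plan that is not at hand. Both are fair. The missing stratified analysis is therefore not the fault. What remains is the inference in 7.6, made without noting the exposure.

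**Conclusion.** The point holds in a limited form. Most 8B girls, about 64% for both active years and about 80% for at least one, were in the schools during active delivery. These shares rest on the planned 36% attrition and stable enrollment, and a majority remains under the variations tried short of 28% class growth. The pooled 8B difference measures persistence of effect in mostly exposed girls. It does not separate carry-over from a maintained environment, and a fall from 8A to 8B does not separate failed maintenance from a different dose. How much carry-over to expect is unknown, although sections 2.5 and 2.6 cite an elementary-school trial whose effects were still detectable in 8th grade, so it cannot be dismissed.

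The primary analysis, aim 9 and the direct environmental measures are unaffected. This is a low-cost improvement to the interpretation of a secondary result. Separately, the timeline in section 4.5 runs intervention activities to 5/15/06, which conflicts with an active phase that ended a year before 8B. Those passages should be reconciled, but the conflict does not rescue the inference.

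**What to change.** In 7.6, and as a clarification in 4.1, state that the pooled 8B intervention-control difference measures persistence of effect in girls most of whom were exposed during the active phase, at a dose different from 8A. State that maintenance of the environment and of the intervention (aim 10) is judged on the direct 8B school measures in sections 10.2 and 10.3.

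Using the entry-grade item already collected at 8B, also report the 8B difference with confidence intervals for girls who entered in 8th grade and for earlier entrants. Label it supportive only: entry grade arises after randomization, entrants mix with peers who were exposed, and precision is low.

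The cost is a few sentences and one stratified analysis, with no new data. The price is a more modest sustainability claim and an imprecise new-entrant estimate.
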